become more ubiquitous in wearable mHealth devices. Data is analyzed on a near-continuous basis for rhythm abnormalities as well as other physiologic parameters. Individuals agreeing to be monitored with the Amiigo will have one sent to them along with a charging device and instructions to download the smartphone app. Only routine fitness data, such as activity, calories burned and sleep duration will be available to Amiigo users via the app. Individuals will be encouraged to wear the device as frequently as possible, night and day, throughout the 4-month monitoring period. Rhythm monitoring will occur passively while a subset will also be prompted daily to sit quietly for 60 seconds to allow for active monitoring. As the Amiigo's rhythm detection capability is exploratory anyone identified to potentially have AF during a period when they are not concurrently wearing a ZIO XT Patch, will be sent another ZIO XT Patch to wear for an additional 2 weeks in order to confirm the diagnosis of AF.

Observational Control Group

A risk-matched observational cohort will be developed from among individuals deemed eligible for study participation but not having the opportunity to participate in the randomized study (i.e. randomized cohort filled prior to their being invited). Individuals will be matched 2:1 with the 2,000 actively monitored cohort based on age, gender, CHA₂DS₂-VASc score, and Propensity Score. An individual's CHA₂DS₂-VASc score can range from 0 to 10 and is based on the composite value of points determined by the presence of cardiac failure or dysfunction (1 point), Hypertension (1 point), Age \geq 75 (2 points), Diabetes (1 point), Stroke (2 points)-Vascular disease (1 point), Age 65–74 (1 point) and Sex category (1 point for female).

The observational period of controls will begin the day their matched actively monitored counterpart signed their informed consent.

Atrial Fibrillation Diagnosis

In the actively monitored cohort a diagnosis of atrial fibrillation/flutter will be made based on documented evidence of a minimum of 30 seconds of continuous atrial fibrillation or flutter confirmed by ECG monitoring with the ZIO XT Patch during the active monitoring period, or the new clinical diagnosis of atrial fibrillation or flutter based on claims data. For the control cohort a new diagnosis will be based solely on a new clinical diagnosis documented in claims data.

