Upon signing the informed consent document, subjects will be randomized to either the immediate monitoring group or delayed monitoring group by random number generator. The random number generator uses Ruby's pseudo-random number generator functionality (PRNG) implemented as a modified Mersenne Twister with a period of 2**19937-1. The subject's group assignment will be sent to the STSI coordinating team. Continued eligibility of all randomized subjects for the study will be confirmed upon enrollment using Aetna databases for all inclusion and exclusion criteria.

For subjects randomized to the immediate monitoring group, the first Zio patch will be sent upon confirmation of continued eligibility. The first Zio patch will be worn by subjects in the immediate monitoring group during the first two weeks of the 4-month monitoring period. A second Zio patch will be sent to subjects in the immediate monitoring group for wear during the final two weeks of the 4-month monitoring period.

A subject will be considered withdrawn from the study if they inform the STSI study coordinating center that they wish to withdraw or if they have not initiated use of the first Zio patch after 3 notifications (e-mail/phone/e-mail) from the coordinating center.

Intention-to-treat analysis for the RCT will include all participants who are enrolled in the study according to their randomly assigned group (immediate monitoring or delayed monitoring) with the RCT follow-up time for subjects in the immediate monitoring group beginning at date of enrollment and ending at 4 months following date of enrollment or the time of completion of monitoring with their final patch, whichever is longest, and for subjects in the delayed monitoring group beginning at date of enrollment and ending at 4 months following the date of enrollment.

The per protocol analysis of the RCT will include immediate monitoring participants had analyzable data from the Zio patch for at least 30 continuous minutes any time during their assigned monitoring period and all participants in the delayed monitoring group who did not withdraw from the study prior to 4 months of follow-up.

Delayed Monitoring Group

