Subjects randomized to the delayed monitoring cohort for the RCT will be actively monitored following completion of the 4 month RCT follow-up period (for which they serve as unmonitored controls). Subjects in the delayed monitoring group will receive their first Zio patch 4 months following their date of enrollment. The first Zio patch will be worn during the first two weeks of the 4-month monitoring period. A second Zio patch will be sent to subjects in the delayed monitoring group for wear during the final two weeks of the 4-month monitoring period.

Matched Observational Cohort Study: Actively Monitored (Immediate and Delayed) vs. Matched Observational Controls

For the Matched Observational Cohort study, the actively monitored group will include all subjects in the RCT who were randomly assigned to either active monitoring period (immediate or delayed).

Two matched controls will be selected for each of the 2,100 actively monitored subjects in the RCT (1,050 immediate + 1,050 delayed) from 1) the pool of subjects from the original eligible cohort who continue to be eligible based on monthly database updates and did not receive an invitation to enroll. Matching will be performed using the following criteria:

- Sex (exact)
- Age (exact by year of birth)
- CHA₂DS₂ VASc score (exact score)

CHA₂DS₂ VASc scores are re-calculated for monitored subjects at time of enrollment (updating scores calculated for eligibility of original pool). CHA₂DS₂ VASc scores are re-calculated for the pools of potential matched controls following the monthly update of the Aetna claims database and immediately prior to application of the matching protocol. Actively monitored subjects and controls will be matched on these updated CHA₂DS₂ VASc scores. Exact matches are prioritized. Matching of CHA₂DS₂ VASc score \pm 1 will be the next option if 2 exact match controls are not found for a monitored subject.

Start date for determination of outcomes from Aetna databases for both monitored subjects and matched controls will be the date of enrollment of the monitored subject. End date for the analysis of prevalence of atrial fibrillation, initiation of anticoagulation and initiation of other AF-specific interventions will be 12 months from the actively monitored subject's date of enrollment (by exact month and day). End date for analysis of outcomes at 3 years will be 3 years from the actively monitored subject's date of enrollment (by exact month and day).

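### Matched controls may be selected and scored on status after their follow-up has started, which would lower control AF and inflate the 12-month detection effect

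*SAP*

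**What the plan says.** All of the following is in SAP Section 4 unless stated.

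- **Start of follow-up.** The start date for outcomes "for both monitored subjects and matched controls will be the date of enrollment of the monitored subject". Protocol Section 4 (Observational Control Group) likewise uses the day the monitored counterpart signed consent.
- **Monitored subjects.** "Continued eligibility of all randomized subjects for the study will be confirmed upon enrollment using Aetna databases". Their CHA2DS2-VASc "scores are re-calculated for monitored subjects at time of enrollment".
- **Controls.** They are drawn from "the pool of subjects from the original eligible cohort who continue to be eligible based on monthly database updates", limited to members who were not invited. Their scores are recalculated "following the monthly update of the Aetna claims database and immediately prior to application of the matching protocol".
- **Who is left to be a control.** The protocol explains the lack of an invitation as "randomized cohort filled prior to their being invited".
- **Exclusions.** Current or prior AF, flutter or atrial tachycardia; chronic anticoagulation; hospice care; and others.

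Neither document gives a matching date, says which monthly update decides a control's eligibility, sets a maximum lag, or says that control status is judged as of the index date.

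**The concern.** Follow-up and eligibility should share one time zero in both groups. Here the monitored subject is checked and scored at enrollment, but the control may be checked and scored at a later update and then given a back-dated start.

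AF is both an exclusion and the main 12-month outcome. A potential control whose AF claim becomes visible between the index date and matching is dropped from the pool. A monitored subject with AF in the same interval stays in and counts as an event. Selecting one group on its future lowers the control rate and favors screening on detection.

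The planned analyses do not repair this. The logistic models in SAP Section 7 adjust for baseline covariates, not for selection on later status. SAP Section 8 only compares Cox models with and without an allowance for the matching.

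**Working it through.** **Order of dates**

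1. Time zero for both groups is the monitored subject's enrollment.
2. The monitored subject's eligibility and score are taken at enrollment.
3. The match uses the score from step 2, so it cannot be run before enrollment.
4. The control's score comes from a monthly update immediately before step 3. Eligibility comes from monthly updates, with no statement of which one.
5. Let L be the time from time zero to the update used. If the last update before enrollment is used, there is no gap. Otherwise L is above zero. The SAP does not bound L.

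**Plausible lag (assumed; not stated in the documents)**

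- Rolling monthly matching, with enrollments spread evenly over the month, gives about 0.5 month on average.
- Matching after the cohort fills depends on the recruitment pace. From SAP Section 4, 2,100 / (10,000 × 5%) = 4.2, so five waves. Four intervals of one to two weeks make 4 to 8 weeks from first to last wave. The protocol's 2,250 gives 4.5, again five waves. Averaged over evenly spaced waves this is 2 to 4 weeks, plus the wait for the next update.

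I therefore use L = 0.5, 1 and 2 months.

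**The plan's own figure**

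SAP Section 7 gives 2,000 vs 4,000 subjects, 7% vs 2%, two-sided alpha 0.05.

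- Pooled rate = (140 + 80) / 6,000 = 3.67%.
- SE under the null = √[0.0367 × 0.9633 × (1/2,000 + 1/4,000)] = 0.00515.
- SE under the alternative = √[0.07 × 0.93/2,000 + 0.02 × 0.98/4,000] = 0.00612.
- z = (0.05 − 1.96 × 0.00515) / 0.00612 ≈ 6.5, so power is above 99%, as stated.

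**Loss of control AF**

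Observed control rate = 2% − h × L, and ratio = 7% / observed control rate. Two values of h follow from the documents:

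- Protocol Section 7: 0.5% over 4 months without monitoring, so h = 0.125 points per month.
- SAP Section 7: 2% spread over 12 months, so h = 0.167 points per month.

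With no gap, 80 of 4,000 controls have AF and the ratio is 3.5.

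| L (months) | h | Control rate | Share lost | Cases lost of 80 | Ratio |
|---|---|---|---|---|---|
| 0.5 | 0.125 | 1.94% | 3.1% | 2.5 | 3.61 |
| 0.5 | 0.167 | 1.92% | 4.2% | 3.3 | 3.65 |
| 1 | 0.125 | 1.875% | 6.25% | 5 | 3.73 |
| 1 | 0.167 | 1.83% | 8.3% | 6.7 | 3.82 |
| 2 | 0.125 | 1.75% | 12.5% | 10 | 4.00 |
| 2 | 0.167 | 1.67% | 16.7% | 13.3 | 4.20 |

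Power stays above 99% in every row, because the bias widens the difference.

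**If there were no true difference**

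With a true rate of 2% in both groups and the higher h, simulated Fisher tests (2,000 runs) gave a significant result favoring screening in 2.1% of trials at L = 0, 6.5% at 1 month and 15% at 2 months, against a nominal 2.5%.

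**Other outcomes**

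- *Anticoagulant initiation.* The exclusion is chronic therapy. The endpoint in SAP Section 5 counts any new fill of a listed anticoagulant, and P2Y12 fills without new acute coronary syndrome. Controls can still have this outcome in the gap, so it is suppressed only in part.
- *Three-year outcomes.* Removing deaths, hospice entries and AF from controls alone can make the control group look healthier, which works against screening.
- *Matching score.* A control's stroke or heart failure after the index date raises the score used for matching, so the match is no longer on baseline status. The stroke can still count as a follow-up event.

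**The case against.** The strongest reply is that the gap is inferred. The SAP refers to monthly updates and to pools of potential controls in the plural, which fits rolling matching, and the update used could be the last one before enrollment, leaving no gap. The idea that the pool is known only when recruitment closes rests on a parenthesis in the protocol; the SAP says only that controls were not invited. This stands as a limit on certainty. It does not dispose of the point, because nothing in the SAP requires the earlier update and the protocol's wording points to a later one.

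It can also be said that monitored subjects are checked after consent too, since the first patch goes out only once continued eligibility is confirmed. The documents do not say how current those data are or how failures are handled. The difference between the groups therefore cannot be sized exactly, and a gap affecting controls alone is not established.

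A further reply is that the 12-month comparison is secondary and the planned difference is large. That is fair. The false-positive figures above need equal true rates, far from the planned 7% vs 2%. What is at risk is mainly the size of the estimate.

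**Conclusion.** The point holds conditionally. As written, the plan allows controls to be selected and scored on status after time zero. To the extent that it does, the 12-month AF detection effect is inflated. For assumed lags of 0.5, 1 or 2 months, about 3-4%, 6-8% or 12.5-17% of control AF is lost, and the planned ratio of 3.5 becomes about 3.6-3.65, 3.7-3.8 or 4.0-4.2. These figures assume a constant rate within the gap, a monitored rate that stays at 7%, and AF claims that are visible in the update used. Claims that arrive late would reduce the loss.

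A reader might infer more than the documents support:

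- That controls must pass a later check and so have zero AF and zero anticoagulation in the gap. The later date is not stated, late claims still count, and the anticoagulation endpoint is wider than the exclusion.
- That the gap could be four months. That exceeds the planned recruitment pace.
- That screening looks better throughout. The direction holds for AF detection and, in part, for treatment starts; 3-year outcomes can be biased the other way.
- That the main result is compromised. The randomized 4-month primary analysis does not use these controls.

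This should be fixed before matching is run. Confidence is medium, because the lag is unknown.

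**What to change.** In SAP Section 4:

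- Assess each control's eligibility, coverage and CHA2DS2-VASc as of the matched monitored subject's enrollment date, using only claims with service dates before it.
- State that no diagnosis, fill, death or disenrollment after that date may remove a control from the pool or change its score.
- Report the distribution of the lag from index date to matching.

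Claims are dated, so index-date status can be rebuilt whenever matching is run. The cost is SAP wording and a little programming. The measured advantage of screening may be slightly smaller. If the sponsor already intends this, a sentence saying so settles the point.

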2. Time to first event of stroke, systemic emboli, or myocardial infarction in the sub-population of individuals diagnosed with AF in the 2 cohorts, as well as within the entire cohorts during 3 years of follow-up. For the Medicare population in who reliable mortality data are available the time to first event of stroke, systemic emboli, myocardial infarction or death will also be evaluated.
 - Time to first event of individual components of the combined endpoint.

3. Cost effectiveness outcome is a key analysis but because of the many unknowns surrounding event rates, and changes in therapy at the time of diagnosis a Bayesian approach seems most appropriate. The initial determination of cost effectiveness will be limited to those diagnosed with AF by 3 years using available claims data. A secondary analysis can evaluate the entire study population comparing a monitored approach to standard of care.
4. Exploratory analysis of the efficacy of the Amigo wristband in detecting AF relative to ECG confirmation by ZIO XT Patch.

Safety Endpoints

1. Incidence of hospitalization for a primary bleeding diagnosis.
2. Incidence of the detection of non-AF, but other actionable heart rhythm issues during monitoring.
3. Incidence, timing and etiology of early discontinuation of active monitoring.

Endpoint Data Dictionary

1. Atrial Fibrillation/Flutter: Diagnosis of atrial fibrillation or atrial flutter confirmed via the Aetna Informatics Health Profile Database (HPD). The HPD is a foundation database used to identify Aetna members with chronic diseases or medical conditions. The identification algorithms are comprised of medical, pharmacy, and clinical laboratory data from physician claims and encounters, specialist claims, pharmacy, facilities, laboratories and others.
2. Each of the end-points listed below will be identified using ICD9/ICD10 codes within the adjudicated inpatient or ER medical case.
 - a. Transient ischemic attack / Stroke
 - b. Myocardial infarction
 - c. Arterial thromboembolism
3. Hospital admitting, discharge and transfer (ADT) information will be used to identify hospitalizations, and length of stay.

4. Drug NDC codes will be used to identify new refill for any anticoagulant (dabigatran, rivaroxaban, apixaban) or P2Y12 antagonists (clopidogrel, prasugrel or ticagrelor).
5. Mortality will be determined based on the latest Aetna membership tables and hospital discharge status.

7. Statistical Considerations

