- b. In the sub-population of individuals newly diagnosed with AF during the 3-year follow-up.

9. Compare time to first event of the combined endpoint of stroke, systemic embolism, myocardial infarction or death among subjects in the Medicare population at baseline in the actively monitored cohort with the matched observational control cohort at 3 years:

- a. In the entire cohorts.
- b. In the sub-population of individuals newly diagnosed with AF during the 3-year follow-up.

10. Compare time to first event of individual components of the combined endpoint (stroke, systemic embolism, myocardial infarction) in the actively monitored cohort with the matched observational control cohort at 3 years:

- a. In the entire cohorts.
- b. In the sub-population of individuals newly diagnosed with AF during the 3-year follow-up.

11. Compare time to first event of all-cause hospitalizations in the actively monitored cohort with the matched observational control cohort at 3 years:

- a. In the entire cohorts.
- b. In the sub-population of individuals newly diagnosed with AF during the 3-year follow-up.

12. Compare total number of all-cause hospitalizations in the actively monitored cohort with the matched observational control cohort at 3 years:

- a. In the entire cohorts.
- b. In the sub-population of individuals newly diagnosed with AF during the 3-year follow-up.

Analysis of Safety Endpoints

1. Compare time to first event of hospitalization for a primary bleeding diagnosis in the actively monitored cohort with the matched observational control cohort at 3 years:
 - a. In the entire cohorts.
 - b. In the sub-population of individuals newly diagnosed with AF during the 3-year follow-up.
2. Compare incidence of the detection of non-AF, but other actionable heart rhythm issues during monitoring in the actively monitored cohort with the matched observational control cohort in the entire cohorts at 3 years.
3. Describe incidence, timing and etiology of discontinuation of active monitoring in the monitored cohort.

Exploratory Analysis

1. Evaluate the correlation between AF detected by the Amiigo wristband with the incidence of AF detected by the Zio patch in active monitoring cohort during 4 months of active monitoring.

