71. Followup Rx Fill for Entresto [Aetna Pharmacy]
72. Followup Rx Fill for Statin or PCSK9 [Aetna Pharmacy]
73. Followup Rx Fill for P2Y12 Receptor Inhibitor [Aetna Pharmacy]
74. Followup Rx Fill for Diabetes Medication [Aetna Pharmacy]
75. Followup Rx Fill for Novel Anticoagulants [Aetna Pharmacy]
76. Followup Rx Fill for Other Anticoagulants [Aetna Pharmacy]
77. Followup Rx Fill for Warfarin [Aetna Pharmacy]
78. Followup Rx Fill for Heparin [Aetna Pharmacy]

Covariates

1. Sex [Aetna Membership Table]
2. Age [Aetna Membership Table]
3. Race/Ethnicity [Aetna Membership Table]
4. Insurance type (Medicare, Commercial or Both) [Aetna Membership Table]
5. Rural/suburban/urban (based on zip code) [Aetna Membership Table; U.S. Census]
6. Region of residence (based on zip code) [Aetna Membership Table; U.S. Census]
7. Median Household Income (based on zip code) [Aetna Membership Table; U.S. Census]
8. CHA₂DS₂ VASc [Aetna Claims Data; Aetna HPD; Calculation in Appendix]
9. Other co-morbidity scores
 - a. Baseline Episode Risk Group (Retrospective) [Aetna Predictive Modeling Table]
 - b. Baseline Episode Risk Group (Prospective) [Aetna Predictive Modeling Table]
 - c. Baseline Charlson Comorbidity Score [Aetna Claims Data]
 - d. Baseline Framingham Score [Aetna Claims Data; Aetna HPD]
10. Baseline months of Aetna Eligibility [Aetna Membership Table]

11. Follow-up months of Aetna Eligibility [Aetna Membership Table]
12. Total device wear time [Zio patch Usage]
13. Analyzable recording time [Zio patch Usage]

Baseline diagnoses:

14. Alcoholism [Aetna HPD]
15. Benign Prostatic Hypertrophy [Aetna HPD]
16. Metastatic Cancer [Aetna Claims Data]
17. Cardiomyopathy [Aetna Claims Data]
18. Cataract [Aetna HPD]
19. Cerebrovascular Disorder [Aetna HPD]
20. Chronic Liver Disease [Aetna HPD]
21. COPD [Aetna HPD]
22. Chronic Renal Failure [Aetna HPD]
23. Chronic Thyroid Disorder [Aetna HPD]
24. Congestive Heart Failure [Aetna HPD]
25. Coronary Artery Disease [Aetna Claims Data]
26. Dementia [Aetna HPD]
27. Depression [Aetna HPD]
28. Diabetes Mellitus [Aetna HPD]
29. Glaucoma [Aetna HPD]
30. Hyperlipidemia [Aetna HPD]
31. Hypertension [Aetna HPD]
32. Anemia [Aetna Claims Data]
33. Ischemic Heart Disease [Aetna HPD]
34. Low Back Pain [Aetna HPD]
35. Nonspecific Gastritis/Dyspepsia [Aetna HPD]
36. Obesity [Aetna HPD]
37. Osteoarthritis [Aetna HPD]
38. Peripheral Vascular Disease [Aetna Claims Data]
39. Obstructive Sleep Apnea [Aetna Claims Data]

Baseline procedures:

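### Controls are not matched on insurance type, so the Medicare-only 3-year composite with death loses some matched controls and its guaranteed balance

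*SAP*

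**What the plan says.** SAP section 4 plans 2:1 matching: "Two matched controls will be selected for each of the 2,100 actively monitored subjects in the RCT". The section goes on to state "Matching will be performed using the following criteria", and its list has three entries. They are exact sex, "Age (exact by year of birth"), and exact CHA2DS2-VASc score. A score within one point "will be the next option if 2 exact match controls are not found for a monitored subject". Insurance type is not among them. The protocol (section 4, Observational Control Group) matches "based on age, gender, CHA₂DS₂-VASc score, and Propensity Score", but does not say what enters the propensity score, and the SAP list leaves it out.

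The same SAP section draws the study population from both commercial and Medicare members. Secondary analysis 9 in SAP section 3 takes the composite that adds death to the vascular events, and makes the comparison "among subjects in the Medicare population at baseline in the actively monitored cohort with the matched observational control cohort at 3 years". Protocol section 6 gives the reason for the restriction: "For the Medicare population in who reliable mortality data are available". Insurance type is already on file, since SAP section 5 lists the covariate "Insurance type (Medicare, Commercial or Both) [Aetna Membership Table"]. SAP section 7 puts it in the 12-month logistic models and the 3-year Cox models.

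Neither document says what happens to a matched set whose members differ in insurance type.

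**The concern.** Analysis 9 is the only listed comparison that includes death. It is run in a subset defined by a variable that the matching ignores. A Medicare participant can be given one or two commercially insured controls, and those controls drop out when the analysis is restricted. Medicare controls drawn for commercial participants may enter without their partners. Balance on age, sex and score, which the match secures in the full cohorts, is then no longer guaranteed in the subset. SAP section 7 checks the match in the full cohorts and requires no between-cohort check among Medicare members.

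Two further gaps follow from the same omission. The 12-month Fisher's exact tests and the 3-year Kaplan-Meier comparisons are unadjusted, so insurance type is left unbalanced by design in analyses that rely on matching alone, although the SAP names it as a potential confounder. And the wording of analysis 9 can be parsed so that the Medicare condition applies to the monitored side only. That would keep commercial controls whose deaths are not reliably recorded.

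**Working it through.** The documents give no Medicare share, sample size or power for analysis 9, so there is no stated figure to reproduce. The nearest 3-year figure is the 81% power in SAP section 7 (200 versus 400, 5% versus 12%). A two-proportion normal approximation returns 81.2%. It concerns the AF sub-population and a composite without death, and does not bear on this point.

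**Inputs.** Two controls per participant (SAP section 4). q = probability that a Medicare participant's matched control is also in Medicare. q is not given; the range 0.95 to 0.70 is an assumption. The two controls are taken as independent.

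**Both cohorts restricted to Medicare (natural reading).**
- Sets losing at least one control: 1 − q²
- Sets losing both: (1 − q)²
- Mean controls kept per participant: 2q
- Relative variance of an unstratified log hazard ratio near the null, using participants and their retained controls: (1 + 1/(2q)) / (1 + 1/2)
- For a Cox model stratified by set, with rare events, a set with k controls carries information proportional to k/(k + 1): 2/3, 1/2 or 0. Relative information is [q²(2/3) + 2q(1 − q)(1/2)] / (2/3) = q² + 1.5q(1 − q), and relative variance is its inverse.

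| q | Lose ≥1 | Lose both | Controls per participant | Variance, unstratified | Variance, stratified by set |
|---|---|---|---|---|---|
| 0.95 | 9.8% | 0.3% | 1.9 | +1.8% | 1/0.974: +2.7% |
| 0.90 | 19% | 1% | 1.8 | +3.7% | 1/0.945: +5.8% |
| 0.80 | 36% | 4% | 1.6 | +8.3% | 1/0.880: +13.6% |
| 0.70 | 51% | 9% | 1.4 | +14.3% | 1/0.805: +24.2% |

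**If q varies by birth year.** For a given mean q, the share losing at least one control is then at most the tabled value, and the share losing both is at least the tabled value. Example (assumed): 80% of sets at q = 1 and 20% at q = 0.5 give a mean of 0.8 + 0.1 = 0.90. At least one control is lost in 0.2 × 0.75 = 15% of sets (not 19%), and both in 0.2 × 0.25 = 5% (not 1%).

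**Commercial controls kept (loose reading).** With equal true mortality and a fraction s of commercial deaths recorded (assumed), the apparent monitored-to-control death ratio is 1/(q + (1 − q)s). For q from 0.95 to 0.70 it is 1.03 to 1.18 at s = 0.5, and 1.05 to 1.43 at s = 0. The bias runs against monitoring.

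**Is the pool large enough for one more criterion?** At the stated 5% uptake, 2,100 enrolments need 2,100/0.05 = 42,000 invitations. That leaves about 58,000 of more than 100,000 eligible members for 2 × 2,100 = 4,200 controls. With the protocol's figure of about 2,250 consents, 45,000 are invited and about 55,000 remain.

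**The case against.** A reader might infer that analysis 9 counts controls whose deaths are missed. The documents do not support that as the plan. The objectives in both documents confine the death composite to the Medicare population, SAP section 5 labels the death endpoint as a Medicare one, and SAP section 7 names Medicare enrollees as the sub-population for it. Only loose syntax in analysis 9 leaves the other parse open, and one sentence closes it.

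A reader might also infer that the analysis loses its matched design and becomes invalid. It does not. The 3-year Cox models adjust for age, sex and co-morbidity scores, and SAP section 8 runs the regular Cox model without using the sets. Only the conditional Cox sensitivity model needs them intact. A retained control still matches its participant on sex, birth year and score, or score within one point. The regular model can also use Medicare controls drawn for commercial participants, so its precision loss may be smaller than tabled.

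Three more points are fair. Exact matching on birth year may already align insurance type in many sets, so q could be high. The protocol's undefined propensity score might have included insurance type. And analysis 9b selects people who develop AF after baseline, which splits sets whatever the match.

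What stands is the gap itself: no criterion and no rule for discordant sets. Adjusting for insurance type cannot repair this inside a Medicare-only subset, where that covariate hardly varies. Nor does it help the unadjusted Fisher and Kaplan-Meier comparisons.

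**Conclusion.** The point holds as a design gap of minor to moderate weight. Under the assumed q of 0.95 to 0.70, up to 10% to 51% of Medicare sets lose at least one control and at least 0.3% to 9% lose both. Variance rises by about 2% to 14% in an unstratified analysis of participants and their retained controls, and by about 3% to 24% if stratified by set. These sizes rest on an unknown q and on independent controls; nothing in the documents fixes where in the range the study lies. The consequences are lost precision, no assurance of exact balance in the Medicare subset, and broken sets in one sensitivity model. Analysis 9 is one of twelve secondary analyses and is not labelled key. The missed-deaths bias would arise only if commercial controls were kept, against the sense of the other sections.

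**What to change.** Add baseline Medicare status (Medicare or Both versus Commercial only), at the participant's enrolment date, to the exact criteria in SAP section 4. State in analysis 9 that both cohorts are restricted to baseline Medicare members, and add a between-cohort balance check in that subset. At the same time, reconcile the protocol's propensity score with the SAP list: define it or remove it.

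If matching has been run and will not be repeated, restrict both cohorts to baseline Medicare members, state the rule for discordant sets, and use the covariate-adjusted Cox model for analysis 9. None of this keeps sets intact in analysis 9b, and the SAP should say so.

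Before matching, the cost is one more criterion on a field already held, with a few more matches at score ±1 or with a single control in sparse cells. After matching, repeating it means replacing some controls and drawing new extracts, so the fallback may be the proportionate choice.
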